Day	-28	1	8	22	43	64	84	98		
Day Visit Window	+7/ -14		±1	±2	±2	±2	±2	±3		
Spot urine from first morning void over 3 consecutive days: albumin, creatinine (central laboratory)		X		X	X		X	X	Spot urine from first morning void over 3 consecutive days, ideally on day of clinic visit and preceding 2 days, collected at home in provided vials. Analysis will be done in all 3 samples at central laboratory and averaged.	Section 8.1.1
Spot urine from first morning void: Na ⁺ , K ⁺ , uric acid, urea, glucose, creatinine, osmolality, and cortisol (central laboratory)		X		X	X		X	X	Spot urine from first morning void, only from the third day sample (day of clinic visit), collected at home in provided vial. Analysis will be done at central laboratory.	Sections 8.5.3 and 8.5.3.1
Body weight	X	X	X	X	X		X	X	Body weight must be taken and reviewed before treatment at each dosing visit.	Sections 8.2.2 and 5.1
Echocardiography	X						X		Screening and Week 12 only. ECHO will be performed locally and sent to central reader. Results need to be available before randomisation.	Section 8.1.3.3
Bioimpedance spectroscopy		X	X	X	X		X	X		Section 8.1.3.2
Home-based monitoring										
Daily digital body weight measurement		Daily home measurement using a digital device from randomisation to end of follow up.							Home body weight measurements should start 2 days before randomisation (same as for spot urine).	Section 8.1.3 and Section 8.2.1

Procedure	Screening	Interventional period							Follow-up	Notes	Details in CSP Section/Appendix
		1	2	3	4	5	6	7 (ED)			
Visit	1	2	3	4	5	6	7 (ED)	8			
Week	-4	0	1	3	6	9	12	14			
Day	-28	1	8	22	43	64	84	98			
Day Visit Window	+7/ -14		±1	±2	±2	±2	±2	±3			
Pharmacodynamics											
Plasma/serum K ⁺ , Na ⁺ , uric acid, BUN, fasting plasma glucose, cystatin C, haematocrit, haemoglobin, ET-1, ELDP, CT-proET-1, copeptin, NT-proBNP, and BNP (central laboratory)	X	X	X	X	X	X	X	X	Results for central BNP testing must be reviewed within 24 hours of receipt by the investigator.	Section 8.2.4 and 8.5.3.1	
BNP or NT-proBNP (local laboratory)	X								Results need to be available before randomisation.	Section 8.2.4	
Safety assessments											
Adverse event review	X SAEs only	X	X	X	X	X	X	X		Section 8.3	
Vital signs (blood pressure, pulse, respiratory rate)	X	X	X	X	X	X	X	X	Vital signs at Visit 2 need to be performed and the results reviewed before randomisation in IWRS.	Section 8.2.2 and 8.1.2.1	

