3.2.1 Efficacy Variables

3.2.1.1 Urinary Albumin to Creatinine Ratio (UACR)

The UACR is a key marker for assessing kidney function. The UACR is a ratio between 2 measured substances (urine albumin and creatinine), which estimates 24-hour urine albumin excretion.

The UACR is calculated as follows:

- $UACR (mg/g) = \text{urine albumin (mg/dL)} / \text{urine creatinine (g/dL)}$

Urine samples for the determination of albumin and creatinine levels and calculation of UACR will be collected at the time points described in the SoA in [Appendix A: Schedule of Activities](#).

Spot urine from first morning void will be collected the day after screening and analysed centrally.

For subsequent visits, participants will collect first morning void samples at home on 3 consecutive days. Samples will be analysed centrally.

At each visit (except for screening), the geometric mean of the triplicate UACRs will be computed and used for all analysis of UACR. If any of the samples for a triplicate UACR is missing, then the geometric mean will be calculated based on the available samples for the triplicate.

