4.2.3 Analysis Visit Windows

All visit-based summaries will use analysis visits. All post-randomisation scheduled and unscheduled visits (excluding Discontinuation visit), will be mapped to an appropriate analysis visit as shown in Table 5.

Table 5 Analysis Visit Windows

CRF Visit	Target Day ¹	Protocol Visit Window ¹	Actual Assessment Day ²	Analysis Visit
Visit 3 (Wk 1)	D8	D7 to D9	D2 to D15	Week 1
Visit 4 (Wk 3)	D22	D20 to D24	D16 to D32	Week 3
Visit 5 (Wk 6)	D43	D41 to D45	D33 to D53	Week 6
Visit 6 (Wk 9)	D64	D62 to D66	D54 to D74	Week 9
Visit 7 (Wk 12)	D84	D82 to D86	D75 to D91	Week 12
Visit 8 (Wk 14)	D98	D95 to D101	D92 to D129	Follow-up

¹Relative to the date of randomisation

²Relative to the date of first dose of study treatment or randomisation date if no first dose

For visit-based summaries, if there is more than one value per participant within a time window, then the closest value will be summarised, or the earliest in the event the values are equidistant from the

nominal visit date. The listings will highlight the value for that participant that went into the summary table, wherever feasible.

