4.10.2.2 Primary Analysis of Primary Objective

The primary efficacy endpoint for this study is the change in log-transformed UACR from baseline to Week 12. As UACR is assumed to follow a log-normal distribution, it will be log-transformed for statistical analysis purposes. The mean log changes in UACR at Week 12 (\hat{Y}_1, \hat{Y}_2) for zibotentan 1.5 mg combined with dapagliflozin 10 mg and dapagliflozin 10 mg alone will be estimated using a mixed model repeated measures [MMRM] method (Weeks 3, 6, 9, and 12). The least squares means will be back transformed to give the geometric mean change from baseline to Week 12. The geometric means will be converted to percentage mean change for Week 12 from baseline on the original scale using the following formula:

$$(\text{GeoMean}(UACR_{\text{Week12-Baseline}}) - 1) \times 100$$

The change in UACR from baseline to Week 12 for zibotentan 1.5 mg combined with dapagliflozin 10 mg compared to the dapagliflozin 10 mg monotherapy arm will be presented as a geometric mean ratio. The analysis model will include the fixed categorical effects of CSP version (Amendment 2

versus pre-Amendment 2), diabetes (DKD versus non-DM CKD), treatment, visit, and treatment-by-visit interaction, plus baseline eGFR strata (≤ 45 versus > 45 mL/min/1.73 m²), log(UACR) and baseline log(UACR)-by-visit interaction. An unstructured covariance structure will be used for the within-participant errors. The denominator degrees of freedom will be estimated using the Kenward-Roger approximation. If the MMRM model does not converge using an unstructured covariance structure, the Toeplitz, first-order autoregressive or compound symmetric covariance structure will be used. If that does not resolve the convergence issues, the analysis will be altered to use an analysis of covariance (ANCOVA) with a missing at random (MAR) multiple imputation (MI) method implemented (Section 4.10.2.3).

The geometric means, along with the conversion to percentage, for change from baseline to Week 12 from the model, and the 90% confidence intervals will be presented. The geometric mean ratio, which is the back-transformed least squares mean difference in change from baseline to Week 12 between two treatment arms, will be converted to adjusted percentage mean change between treatment arms as follows:

$$[(\text{Geometric Mean Ratio} - 1) \times 100]$$

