Appendix A: Schedule of Activities

Schedule of Activities (Part B)

Procedure	Screening	Interventional period						Follow-up	Notes
		1	2	3	4	5	6		
Visit	1								
Week	-4	0	1	3	6	9	12	14	
Day	-28	1	8	22	43	64	84	98	
Day Visit Window	+7/ -14		±1	±2	±2	±2	±2	±3	
Informed consent	X								
Inclusion and exclusion criteria	X	X							Recheck clinical status before randomisation.
Screening in IRT/RTSM	X								
Randomisation in IRT/RTSM		X							Diaries will be given to the participants and they will be asked to fill in the dose intake information (date and time) at home.
Routine clinical procedures									
Demography and baseline characteristics (smoking history and alcohol consumption included)	X								
Physical examination	X	X	X	X	X	X	X	X	A complete physical examination will be done at screening, randomisation and Week 12. A brief physical examination will be done at Weeks 1, 3, 6, 9, 14.
Medical/surgical history, which includes substance usage and family history of premature cardiovascular disease	X								Substances: drugs, alcohol, tobacco, and caffeine

TP-GDO-WW-016-08

Effective Date: 26 Nov 19

Related to: SOP-GDO-WW-019

CONFIDENTIAL

Project Document Version No. 2.3

Project Document Effective Date: Date of last signature

Page 49 of 59

Parexel International

AstraZeneca
D4325C00001

Statistical Analysis Plan

Procedure	Screening	Interventional period						Follow-up	Notes
		2	3	4	5	6	7 (ED)		
Visit	1						8		
Week	-4	0	1	3	6	9	14		
Day	-28	1	8	22	43	64	98		
Day Visit Window	+7/ -14		±1	±2	±2	±2	±2		
Height	X								
Serology (HIV I and II, Hepatitis B surface antigen, Hepatitis C virus antibody, central lab)	X							Results need to be available before randomisation.	
FSH/LH and serum pregnancy test (females only, central lab)	X							Results need to be available before randomisation.	
Local test for SARS-CoV-2	X							Testing is also required if participants show COVID-19 symptoms during the study.	
Concomitant medication	X	X	X	X	X	X	X		
Efficacy assessments									
Spot urine from first morning void: albumin and creatinine (central lab)	X								Results need to be available before randomisation. A single sample for analysis is sufficient at screening.

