Spot urine from first morning void over 3 consecutive days: albumin, creatinine (central lab)		X		X	X	X	X	X	Spot urine from first morning void over 3 consecutive days, ideally on day of clinic visit and preceding 2 days, collected at home in provided vials. Analysis will be done in all 3 samples at central laboratory and averaged.
Spot urine from first morning void: Na ⁺ , K ⁺ , uric acid, urea, glucose, creatinine, osmolality, and cortisol (central lab)		X		X	X	X	X	X	Spot urine from first morning void, only from the third day sample (day of clinic visit), collected at home in provided vial. Analysis will be done at central laboratory.

TP-GDO-WW-016-08

Effective Date: 26 Nov 19

Related to: SOP-GDO-WW-019

CONFIDENTIAL

Project Document Version No. 2.3

Project Document Effective Date: Date of last signature

Page 50 of 59

Parexel International

AstraZeneca
D4325C00001

Statistical Analysis Plan

Procedure	Screening	Interventional period							Follow-up	Notes
		2	3	4	5	6	7 (ED)	8		
Visit	1								8	
Week	-4	0	1	3	6	9	12	14		
Day	-28	1	8	22	43	64	84	98		
Day Visit Window	+7/ -14		±1	±2	±2	±2	±2	±3		
Body weight	X	X	X	X	X	X	X	X	X	Body weight must be taken and reviewed before treatment at each dosing visit.
Echocardiography	X						X			Screening and Week 12 only. ECHO will be performed locally and sent to central reader.
Bioimpedance spectroscopy		X	X	X	X	X	X	X	X	
Home-based monitoring										
Daily digital body weight measurement		Daily home measurement using a digital device from randomisation to end of follow up.								Home body weight measurements should start 2 days before randomisation (same as for spot urine).
Pharmacodynamics										
Plasma/serum K ⁺ , Na ⁺ , uric acid, BUN, fasting plasma glucose, cystatin C, haematocrit, haemoglobin, ET-1, ELDP, CT-proET-1, copeptin, NT-proBNP, and BNP (central lab)		X	X	X	X	X	X	X	X	Results for central BNP testing must be reviewed within 24 hours of receipt by the investigator.
BNP or NT-proBNP (local laboratory)	X									Results need to be available before randomisation.
Safety assessments										
Adverse event review	X SAEs only	X	X	X	X	X	X	X	X	
Vital signs (blood pressure, pulse, respiratory rate)	X	X	X	X	X	X	X	X	X	Vital signs at Visit 2 need to be performed and the results reviewed before randomisation in IWRS.

TP-GDO-WW-016-08

Effective Date: 26 Nov 19

Related to: SOP-GDO-WW-019

CONFIDENTIAL

Project Document Version No. 2.3

Project Document Effective Date: Date of last signature

Page 51 of 59

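### Does the primary MMRM rely on a Week 9 UACR visit that the protocol does not schedule?

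*SAP*

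**What the plan says.** SAP Section 4.10.2.2 names the visits in the primary model: "mixed model repeated measures [MMRM] method (Weeks 3, 6, 9, and 12". The SAP's UACR section gives no weeks of its own; samples for "calculation of UACR will be collected at the time points described in the SoA", which in the SAP is Appendix A. The row there, "Spot urine from first morning void over 3 consecutive days: albumin, creatinine (central lab", carries a mark at Visit 6.

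Protocol Section 8.1.1 also defers to its schedule, and Section 9.4.2.1 describes the MMRM without naming visits. The protocol's position on Week 9 therefore rests on the Table 1 row "Spot urine from first morning void over 3 consecutive days: albumin, creatinine (central laboratory", which in the copy read here is blank at Visit 6.

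SAP Section 4.15 records several departures from the protocol (among them echocardiography, imputation, MMRM in place of ANCOVA, loss to follow-up and the ambulatory BP set) but nothing on UACR visits. The protocol change tables for the current amendment and for Amendments 1 and 2 show no change to the UACR visits.

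**The concern.** A repeated-measures model that names a visit with no scheduled sample is an inconsistency in the primary analysis. An empty level does no harm, but a nearly empty one could. SAP Section 4.2.3 states: "All post-randomisation scheduled and unscheduled visits (excluding Discontinuation visit), will be mapped to an appropriate analysis visit". The Week 9 window is D54 to D74, so a late Visit 5 or early Visit 7 sample would be labelled Week 9. With only a few such samples the unstructured fit may not converge. Section 4.10.2.2 then moves to Toeplitz, first-order autoregressive or compound symmetric structures. In their standard form these assume one variance for all visits, so the Week 12 standard error could be wrong. The imputation models in Sections 4.10.2.3 and 4.10.2.5 would also take in a sparse Week 9 variable.

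**Working it through.** **1. The rows side by side (visit, with week in brackets)**

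| Row | 1 (-4) | 2 (0) | 3 (1) | 4 (3) | 5 (6) | 6 (9) | 7 (12) | 8 (14) |
|---|---|---|---|---|---|---|---|---|
| Protocol UACR, triplicate | | X | | X | X | | X | X |
| SAP Appendix A UACR, triplicate | | X | | X | X | X | X | X |
| Protocol body weight | X | X | X | X | X | | X | X |
| Protocol vital signs | X | X | X | X | X | X | X | X |

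The body-weight row shows why the protocol blank cannot be taken at face value. Its note reads "Body weight must be taken and reviewed before treatment at each dosing visit", and the study-intervention row says the dose at Visit 6 is taken in the clinic, yet the Visit 6 cell is blank. Appendix A is no cleaner a witness. It is headed "Schedule of Activities (Part B", and its body-weight row prints nine marks for eight visits. Its UACR row does have eight cells and agrees with the SAP text.

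**2. What each case does to the primary model**

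An unstructured covariance has k(k+1)/2 parameters: 4 × 5 / 2 = 10 for four visits and 3 × 4 / 2 = 6 for three. Treatment-by-visit cells over three arms are 12 and 9.

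- Visit 6 is marked in the source: the SAP model is right as written.
- Visit 6 is not marked and no samples fall in D54 to D74: the level does not exist in the data and the fit is the three-visit model. The Week 12 contrast, alpha and sample size are the same.
- Visit 6 is not marked and some samples fall there: see steps 3 and 4.

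**3. How a sample could land in Week 9**

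From SAP Table 5, a Visit 5 sample must be 54 − 45 = 9 days or more past its protocol window, or a Visit 7 sample 82 − 74 = 8 days or more before its window. Both windows are ±2 days. Discontinuation visits and data after an intercurrent event are excluded, and the protocol describes no unscheduled on-treatment UACR sampling. The documents give no off-window rate. For assumed rates of 0.5%, 1% and 2%, with 150 + 77 + 150 = 377 evaluable participants (protocol Section 9.2) and two visits each, 754 samples give 3.8, 7.5 and 15.1 strays. The SAP's 75 in the low-dose arm gives 375 and nearly the same counts.

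**4. What the fallback could do to the Week 12 standard error**

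The planning SD is redacted and no correlations are given, so these SDs are assumptions. If one pooled variance replaces the visit-specific ones, the SE ratio at Week 12 is about √(mean variance over Weeks 3, 6, 12) / SD at Week 12, and one-sided alpha is 1 − Φ(1.645 × ratio).

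- SD rising 0.60, 0.65, 0.75: √[(0.3600 + 0.4225 + 0.5625)/3] / 0.75 = 0.670/0.75 = 0.89; alpha 7.1%.
- SD flat: ratio 1.00; alpha 5.0%.
- SD falling 0.75, 0.70, 0.60: √[(0.5625 + 0.4900 + 0.3600)/3] / 0.60 = 0.686/0.60 = 1.14; alpha 3.0%.

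Simulation of the Toeplitz and compound symmetric fallbacks under the same kind of assumptions gave 6.6–6.7%, 5.5% and 2.9–3.0%. The error can go either way, and nothing in the documents supports a direction. Where every unstructured fit converged, the Week 12 SE with and without the sparse Week 9 level had a ratio of 0.992 to 1.001 (5th to 95th percentiles).

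**The case for a change.** The best argument for a change is that the blank may be real and the trigger count is small. In the same protocol block echocardiography falls exactly on screening and Week 12, as its note requires. The stored-sample rows on a later page are also blank at Visit 6, while the row "Vital signs (blood pressure, pulse, respiratory rate" is marked there, so the copy has not simply lost that column. In simulation, 8 off-window samples replacing Visit 5 or Visit 7 stopped the unstructured fit from converging in 75% of 200 runs, and 8 is about what a 1% off-window rate would give. A short wording edit would remove the risk.

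Part of this stands: the blank could be genuine, and a sparse level is awkward for an unstructured model. But the 1% rate, SDs and correlations are assumed, and the fitting routine was neither the SAS procedure nor used with the Kenward-Roger adjustment that the SAP specifies. Failure fell to 4.5% with 15 such samples and 0% with 30. About 52 − 26 = 26 participants in the retained arms were randomised before Amendment 2 and followed the Amendment 1 schedule, which is not shown. If that schedule collected Week 9 UACR, the level would not be sparse. Nor is the edit free: dropping Week 9 from the model and only listing those samples would discard usable on-treatment data.

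**Conclusion.** No change to the plan is needed. The mismatch is real in the copy read here, but it is a clerical query about one schedule cell: is Visit 6 marked for UACR in the source of protocol Table 1? Anyone building the analysis dataset will see at once whether Week 9 samples were collected, and the model follows the data. If they were, the SAP is correct; if there are none, the level disappears. In both cases the Week 12 estimand, sample size and expected precision are essentially the same.

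The remaining case needs several things together: a genuine blank, a handful of samples at least 8 or 9 days outside a ±2-day window, a failed fit, a single-variance fallback and variances that change over visits. Under assumed SDs the one-sided error then lies between 2.9% and 7.1% against a nominal 5%, and near 5% if the variance is flat. These figures are conditional on the assumptions and are not evidence of a defect. If the source check shows a true blank, aligning the visit list is an editorial matter. Week 9 would stay for blood pressure and eGFR, and stray UACR samples could be mapped to the nearest scheduled UACR visit so that none are lost.

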4.2.5 Japan-Specific Analysis

A subset of the planned outputs will be repeated for participants from Japan, as required for interactions with the Japanese Regulatory Agency. The outputs will be identified in the TLF mock shells.

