4.10.3 Analysis of Secondary Objectives Other Than UACR

The secondary efficacy variables will be based on a similar estimand to the primary estimand for the primary objective in Section 4.10.2.1, with the variable and population-level summary updated to be relevant to the secondary efficacy variable specified.

Office systolic and diastolic BP

The change from baseline to Week 12 in office systolic and diastolic BP will be assessed for doses of zibotentan combined with dapagliflozin 10 mg compared to dapagliflozin 10 mg monotherapy. This will be analysed using the MMRM method specified in Section 4.10.2.2, adjusting for the same variables, though with baseline BP replacing baseline log(UACR). The FAS will be used for this analysis and BP will be evaluated on the original scale.

The results of each MMRM will be presented by treatment arm. A summary of change from baseline of office systolic and diastolic BP results will be presented by treatment arm and a by-participant listing of office systolic and diastolic BP results at each visit will be provided. Plots of the mean office systolic and diastolic BP over time up to follow-up visit will be presented.

As a sensitivity analysis, a MMRM will be performed for office systolic and diastolic BP up to Week 12, analysed on the PPS, similarly to that described above.

eGFR

The effect of different doses of zibotentan and dapagliflozin in combination compared to dapagliflozin 10 mg monotherapy on eGFR will be determined from the change in eGFR from baseline to Week 1, from baseline to Week 12, from baseline to Week 14 and from Week 1 to Week 12. Change from baseline to Week 1, baseline to Week 12, baseline to Week 14 and Week 1 to Week 12 will be analysed using the MMRM methodology specified in Section 4.10.2.2. Change from baseline to Week 1, change from baseline to Week 3, change from baseline to Week 6, change from baseline to Week 9, change from baseline to Week 12 and change from baseline to Week 14 will be included in the model, adjusting for the fixed categorical effects of CSP version (Amendment 2 versus pre-Amendment 2), diabetes (DKD versus non-DM CKD), treatment visit, and treatment-by-visit interaction, plus the continuous covariates of baseline eGFR and baseline eGFR-by-visit interaction. The FAS will be used for these analyses and eGFR will be evaluated on the original scale.

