4.14 Determination of Sample Size

With a 1-sided type I error rate of 5%, 150 evaluable participants in the zibotentan 1.5 mg and dapagliflozin 10 mg arm and dapagliflozin 10 mg monotherapy arm will have approximately [REDACTED]% power to detect a dapagliflozin-corrected UACR reduction of [REDACTED]% or more assuming a SD of [REDACTED] on the natural log-scale. In the DKD sub-population (which will be about 70% of the total population), the power to detect the same reduction is estimated to be [REDACTED]%.

For the dose-response models (not part of CSR), the sample size below will have at least [REDACTED]% power across multiple dose-response models to detect dose-response significance. This assumes a 1-sided type I error of 5% and a maximum UACR reduction of [REDACTED]% for the zibotentan 1.5 mg and dapagliflozin 10 mg combination arm relative to dapagliflozin 10 mg.

- Zibotentan/Dapagliflozin dose = 0/10 mg: n = 150.
- Zibotentan/Dapagliflozin dose = 0.25/10 mg: n = 75.
- Zibotentan/Dapagliflozin dose = 1.5/10 mg: n = 150.

A total of 495 participants will be randomised into this study, including participants randomised under the earlier design. Four hundred and fifteen (415) participants will be randomised, accounting for 10% drop-outs, to have the following number of participants in the main analysis (marked as M in

Table 4): 166 participants in the zibotentan 1.5 mg/dapagliflozin 10 mg combination arm and dapagliflozin 10 mg monotherapy arm, and 83 participants in the zibotentan 0.25 mg/dapagliflozin 10 mg combination arm.

A participant is considered to be evaluable if the participant received at least one dose of study intervention, has baseline UACR, and at least one post-treatment UACR result available.

The sample size was calculated using nQuery (version 8.2.0.0) for the pairwise comparisons. The sample size was calculated using the “DoseFinding” package (version 0.9-16) in R (version 3.5.3) for the dose-response models.

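### If the unstructured MMRM fails to converge, every fallback covariance in SAP 4.10.2.2 assumes one variance at all visits, in no fixed order; if spread rises to Week 12, the 5% test is too liberal

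*SAP*

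**What the plan says.** SAP 4.10.2.2 models log(UACR) change at Weeks 3, 6, 9 and 12, with treatment and baseline log(UACR) each crossed with visit. The first choice of covariance is free: "An unstructured covariance structure will be used for the within-participant errors". On inference it says "The denominator degrees of freedom will be estimated using the Kenward-Roger approximation". No empirical (sandwich) standard error is mentioned.

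If the unstructured fit does not converge, "the Toeplitz, first-order autoregressive or compound symmetric covariance structure will be used". The three are joined by a bare alternative. No order is stated, and nothing says which result is reported if several converge. No heterogeneous-variance version is named. If these also fail, the analysis becomes ANCOVA after multiple imputation under MAR (SAP 4.10.2.3). That analysis is otherwise run as a sensitivity analysis.

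The hypothesis in SAP 4.10.1.1 concerns Week 12 only, one-sided at 0.05. Correspondingly, "the 90% confidence intervals will be presented".

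Blood pressure and eGFR borrow the same rules. SAP 4.10.3 says the eGFR changes "will be analysed using the MMRM methodology specified in Section 4.10.2.2", with Weeks 1, 3, 6, 9, 12 and 14 in the model.

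**The concern.** An unstructured matrix gives each visit its own variance. Toeplitz, first-order autoregressive and compound symmetry, in standard form, all replace these by one common variance. The plan therefore drops from full flexibility to equal variances in one step, although structures in between exist.

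This matters because only Week 12 is tested. Treatment and baseline are crossed with visit, so with near-complete data the Week 12 contrast is essentially the same whichever covariance is fitted, and its true variability is set by the Week 12 residual variance. The fallback standard error uses the common variance. If spread is larger at Week 12 than on average, the standard error is too small, the 90% interval is too narrow and the one-sided 5% level is exceeded. Kenward-Roger does not help: it adjusts for estimating the covariance parameters, taking the chosen structure as correct.

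The missing order is a separate gap. A fallback is invoked only once data are in hand, so the rule has to be complete beforehand.

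For eGFR the visit gaps are 2, 3, 3, 3 and 2 weeks. Toeplitz and AR(1) by visit number treat these as equal.

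**Working it through.** **Inputs from the documents**
- Error rate and sample size (SAP 4.14): "With a 1-sided type I error rate of 5%, 150 evaluable participants" per main arm. SAP 4.14 also gives 10% drop-out and 166, 166 and 83 randomised.
- Visits (SAP 4.10.2.2): Weeks 3, 6, 9 and 12, tested at Week 12.
- SD: redacted. No SD by visit and no within-participant correlation is given.

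**The plan's own figures.** One-sided 5% corresponds to z = 1.645, the same z as a two-sided 90% interval, so the two are consistent. 150/0.90 = 166.7 against 166 stated, and 75/0.90 = 83.3 against 83 stated. Power cannot be reproduced because its inputs are redacted.

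**Formula.** With near-complete data and visit-specific treatment and baseline terms:

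- SE ratio = √(common variance / Week 12 variance)
- one-sided size = 1 − Φ(1.645 × SE ratio)
- 90% interval coverage = 1 − 2 × size

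Under compound symmetry the common variance is the average of the visit variances. The values to which AR(1) and Toeplitz converge change the size by no more than about 0.4 points over the ratios examined.

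**Assumption.** The residual SD changes linearly from Week 3 to Week 12. Only the ratio of the two matters. Example at 1.6: SDs 1, 1.2, 1.4, 1.6; variances 1, 1.44, 1.96, 2.56; mean 6.96/4 = 1.74; SE ratio √(1.74/2.56) = 0.824; 1.645 × 0.824 = 1.356; size 8.8%.

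| Week 12 SD ÷ Week 3 SD (assumed) | Mean variance (Week 3 = 1) | SE ratio | One-sided size | 90% CI coverage |
|---|---|---|---|---|
| 0.75 | 0.774 | 1.173 | 2.7% | 95% |
| 1.0 | 1.000 | 1.000 | 5.0% | 90% |
| 1.1 | 1.104 | 0.955 | 5.8% | 88% |
| 1.33 | 1.372 | 0.881 | 7.4% | 85% |
| 1.6 | 1.740 | 0.824 | 8.8% | 82% |
| 2.0 | 2.389 | 0.773 | 10.2% | 80% |

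**Simulation check.** REML fits used 415 participants at 166/166/83, 10% monotone drop-out, the SAP covariates, a normal critical value and 1,500 runs per scenario.

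| SD ratio | Compound symmetry | AR(1) | Toeplitz | Heterogeneous compound symmetry |
|---|---|---|---|---|
| 1.0 | 5.0% | 5.1% | 5.0% | 4.9% |
| 1.3 | 8.2% | 8.1% | 8.2% | 5.8% |
| 1.6 | 9.4% | 9.2% | 9.3% | 6.7% |
| 2.0 | 10.1% | 9.7% | 9.9% | 4.5% |

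The Monte Carlo standard error is about 0.6 points at 5% and about 0.7 near 8%. The three planned fallbacks agree with the formula within simulation error. The heterogeneous column is close to nominal. Its 6.7% is about three standard errors above 5%, but there is no trend across ratios and 2.0 gives 4.5%. It supports the remedy without proving an exact 5%.

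**Number of visits.** The UACR row of the protocol's schedule, as extracted, has no Week 9 mark, whereas the SAP's schedule has one. Extraction may be the cause. With three visits the sizes are 9.2% at ratio 1.6 and 10.8% at 2.0, so the conclusion does not depend on it.

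**The case against.** **The trigger is remote.** This stands. The primary UACR model pools about 415 participants over at most four visits, which means ten unstructured covariance parameters. Nothing suggests it will fail. The eGFR model has six visits and 21 parameters, so failure is somewhat more plausible there. But SAP 4.10.1.1 sets out hypothesis tests only for UACR, so for eGFR the consequence is interval width and not a type I error rate.

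**The size is assumed.** This also stands. A reader might infer from the 1.6 row that 9% is a ceiling. It is not: a doubling of the SD gives about 10%, a rise of 10% to 33% gives about 6% to 7%, and a fall makes the test conservative. The documents do not say that variability grows with time.

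**A check is planned.** The multiple-imputation ANCOVA at Week 12 uses only the Week 12 residual variance, so a large gap between the two standard errors would show. That is a partial check, because the equal-variance MMRM would remain the primary result.

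**Small subsets.** A reader might expect the fallback mainly in the interim, subgroup or Japan outputs. The documents give little support. The interim efficacy analysis uses UACR to Week 6, hence two visits and three parameters. Subgroup estimates come from models with an interaction term, and SAP 4.10.1.3 rules out formal testing within subgroups. For Japan, "A subset of the planned outputs will be repeated for participants from Japan", but the SAP does not say that an MMRM is among them.

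**Choosing after seeing results.** The switch is triggered by non-convergence, and the three structures give nearly the same size, so little could be gained by choosing among them. A reader might also take the order of listing as the intended order. The sentence does not say so, and the gap in pre-specification remains.

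**Conclusion.** The concern holds, conditionally and at low priority. If the unstructured fit fails, the plan offers only equal-variance structures with model-based standard errors and no stated order. The one-sided 5% test at Week 12 would then run at about 6% to 10% for a Week 12 SD 1.1 to 2 times that at Week 3, and at about 3% for 0.75 times. These figures rest on an assumed linear change in SD, near-complete data in the formula (10% drop-out in the simulation), and the standard equal-variance form of each structure.

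The documents do not support saying that the primary analysis as planned is anti-conservative. While the unstructured model converges, this issue does not arise. The case for acting is that the rule is easy to improve before it is needed.

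**What to change.** Replace the fallback sentence in SAP 4.10.2.2 by a fixed sequence: heterogeneous Toeplitz, then heterogeneous AR(1), then heterogeneous compound symmetry. Report the first that converges, keep Kenward-Roger, and if none converges go to the multiple-imputation ANCOVA already planned.

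In SAP 4.10.3, for eGFR, go straight from unstructured to heterogeneous compound symmetry, because the visits are unequally spaced.

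Empirical standard errors for structured fits, with a stated degrees-of-freedom method in place of Kenward-Roger, are an optional addition. They should not be used in small subsets, where they can themselves be unstable.

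**Cost.** Text only: no change to data, visits or sample size. Each heterogeneous structure has one variance per visit instead of one in all, hence three more parameters with four visits (7 against 4 for Toeplitz, 5 against 2 for AR(1) and compound symmetry) and five more with six visits (7 against 2 for compound symmetry). That makes them slightly harder to fit than the structures replaced, though still well below the unstructured 10 and 21.
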